**Table 14 Management and Dose Modification Guidelines for Visual Changes and/or Ophthalmic Examination Findings**

CTCAE Grade a	Adverse Event Management	Action and Dose Modification
Grade 1 bc	
 
Consult ophthalmologist within 7 days of onset
 
	
 
If dilated fundus examination cannot be performed within 7 days of onset, interrupt trametinib until RPED and RVO can be excluded by retina specialist/ophthalmologist. If subject is receiving trametinib/dabrafenib combination therapy dabrafenib may be continued.
 
If RPED and RVO excluded, continue (or restart) trametinib at same dose level.
 
If RPED suspected or diagnosed; see RPED dose modification Table 15 below; report as SAE if diagnosed.
 
If RVO diagnosed: Permanently discontinue trametinib and report as SAE.
 

Grade 2 c and Grade 3 c	
 
Consult ophthalmologist immediately
 
Interrupt trametinib. If subject is receiving trametinib/dabrafenib combination therapy dabrafenib may be continued.
 
	
 
If RPED and RVO excluded, restart trametinib at same dose level.
 
If RPED diagnosed, see RPED dose modification Table 15 below; report as SAE.
 
If RVO diagnosed: Permanently discontinue trametinib and report as SAE.
 

Grade 4 c	
 
Consult ophthalmologist immediately
 
Interrupt trametinib. If subject is receiving trametinib/dabrafenib combination therapy dabrafenib may be continued.
 
	
 
If RPED and RVO excluded, may consider restarting trametinib at same or reduced dose after discussion with study medical monitor
 
If RVO or RPED diagnosed, permanently discontinue trametinib and report as SAE.
 

Abbreviations: RPED = retinal pigment epithelial detachment; CTCAE = Common Terminology Criteria for Adverse Events; RVO= retinal vein occlusion; SAE = serious adverse event

- Refers to CTCAE Version 4.0 'Eye disorders – Other, specify'
- If visual changes are clearly unrelated to study treatment (e.g., allergic conjunctivitis), monitor closely but ophthalmic examination is not required.
- Blood sample for PK analysis should be drawn as close as possible to the time of the event.

**Table 15 Recommended dose modifications for trametinib for retinal pigment epithelial detachments (RPED)a**

CTCAE Grade	Action and Dose Modification
Grade 1 RPED (Asymptomatic; clinical or diagnostic observations only)	
 
Continue treatment with retinal evaluation monthly until resolution. If RPED worsens follow instructions below
 

Grade 2-3 RPED (Symptomatic with mild to moderate decrease in visual acuity; limiting instrumental ADL)	
 
Interrupt trametinib
 
Retinal evaluation monthly
 
If improved to <math>\leq</math> Grade 1, restart trametinib at lower dose (reduced by 0.5 mg) or discontinue in patients taking trametinib 1 mg daily
 

a) Refers to CTCAE Version 4.0 'Retinopathy'

#### 5.8.5.5. Guidelines for Pneumonitis

Pneumonitis has been observed in subjects receiving trametinib, dabrafenib, and in dabrafenib in combination with trametinib. To reduce the risk of pneumonitis, subjects will be monitored closely for symptoms, evaluated with imaging and functional tests. Dose modification and supportive care guidelines for pneumonitis are described in [Table 16](#).

**Table 16 Management and Dose Modification Guidelines for Pneumonitis**

CTCAE Grade	Adverse Event Management	Action and Dose Modification
Grade 1	
 
• CT scan (high- resolution with lung windows) recommended
 
• Clinical evaluation and laboratory work-up for infection
 
• Monitoring of oxygenation via pulse-oximetry recommended
 
• Consultation of pulmonologist recommended
 
	
 
• Continue trametinib at current dose
 

Grade 2	
 
• CT scan (high- resolution with lung windows)
 
• Clinical evaluation and laboratory work-up for infection
 
• Consult pulmonologist
 
• Pulmonary function tests –if < normal, repeat every 8 weeks until <math>\geq</math> normal
 
• Bronchoscopy with biopsy and/or BAL recommended
 
• Symptomatic therapy including corticosteroids if clinically indicated
 
	
 
• Interrupt trametinib until recovery to grade <math>\leq 1</math>
 
• Restart with trametinib be reduced by one dose level
 
• Escalation to previous dose level after 4 weeks and consultation with medical monitor possible
 
• If no recovery to grade <math>\leq 1</math> within 4 weeks, permanently discontinue trametinib
 

Grade 3	
 
• CT scan (high- resolution with lung windows)
 
• Clinical evaluation and laboratory work-up for infection
 
• Consult pulmonologist
 
• Pulmonary function tests-if < normal, repeat every 8 weeks until <math>\geq</math> normal
 
• Bronchoscopy with biopsy and/or BAL if possible
 
• Symptomatic therapy including corticosteroids as clinically indicated
 
	
 
• Interrupt trametinib until recovery to grade <math>\leq 1</math>
 
• After consultation with medical monitor, trametinib may be restarted reduced by one dose level
 
• If no recovery to grade <math>\leq 1</math> within 4 weeks, permanently discontinue trametinib treatment
 

Grade 4	
 
• Same as grade 3
 
	
 
• Permanently discontinue trametinib
 

BAL= bronchioalveolar lavage; CT = computed tomography; CTCAE = Common Terminology Criteria for Adverse Events

## 5.9. Monitoring, Interruption, and Stopping Criteria for Hepatobiliary Events

### 5.9.1. Liver Chemistry Stopping Criteria

These liver chemistry stopping and follow-up criteria have been designed to assure subject safety and evaluate liver event etiology in alignment with the FDA Guidance for Industry – Drug-Induced Liver Injury: Premarketing Clinical Evaluation (July 2009, [www.fda.gov](http://www.fda.gov)).

**Liver chemistry stopping criteria 1-5 are defined as:**

1. ALT  $\geq 3$ xULN and bilirubin  $\geq 2$ xULN (>35% direct bilirubin) (or ALT  $\geq 3$ xULN and INR >1.5, if INR measured)

NOTE: If serum bilirubin fractionation is not immediately available, study treatment should be discontinued if ALT  $\geq 3$ xULN and bilirubin  $\geq 2$ xULN. Serum bilirubin fractionation should be performed if testing is available. If testing is unavailable, record presence of detectable urinary bilirubin on dipstick, indicating direct bilirubin elevations and suggesting liver injury.

2. ALT  $\geq 8$ xULN
3. ALT  $\geq 5$ xULN but <8 xULN persists for  $\geq 2$  weeks
4. ALT  $\geq 3$ xULN if associated with the appearance or worsening of symptoms of hepatitis or hypersensitivity such as fatigue, nausea, vomiting, right upper quadrant pain or tenderness, pyrexia, rash or eosinophilia.
5. ALT  $\geq 5$ xULN but <8 xULN and cannot be monitored weekly for >2 weeks.

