**Table 2 Definitions for Adequate Baseline Organ Function**

System	Laboratory Values
Hematologic	
ANC	$\geq 1.2 \times 10^9/L$
Hemoglobin	$\geq 9$ g/dL
Platelet count	$\geq 100 \times 10^9/L$
PT/INR a and PTT	$\leq 1.3 \times$ ULN
Hepatic	
Total bilirubin	$\leq 1.5 \times$ ULN c
AST and ALT	$\leq 2.5 \times$ ULN
Renal	
Serum creatinine b	$\leq 1.5$ mg/dL
Cardiac	
Left Ventricular Ejection fraction (LVEF) d	$\geq$ LLN by ECHO

Abbreviations: ALT = alanine transaminase; ANC = absolute neutrophil count; AST = aspartate aminotransferase; INR = international normalized ratio; LLN = lower limit of normal; PT = prothrombin time; PTT = partial thromboplastin time; ULN = upper limit of normal.

- a) Subjects receiving anticoagulation treatment may be allowed to participate with INR established within the therapeutic range prior to enrollment.
- b) If serum creatinine is  $> 1.5$  mg/dL, calculate creatinine clearance using standard Cockcroft-Gault formula ([Appendix 4](#)). Creatinine clearance must be  $\geq 50$  mL/min to be eligible.
- c) Except subjects with known Gilbert's syndrome.
- d) ECHO scans must be used throughout the study

10. Women of childbearing potential must have a negative serum pregnancy test within 14 days prior to enrollment and agree to use effective contraception, as defined in [Section 7.4.3.1](#) from 7 days prior to enrollment, throughout the treatment period, and for 4 months after the last dose of study treatment.

11. 

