**Table 3 Categories of Dose Modification Guidelines**

Adverse Event	Dabrafenib	Trametinib	Section
---------------	------------	------------	---------

General Guidelines for Clinically Significant	X	X	5.8.2
Guidelines for Specific Adverse Events			
Cardiovascular Adverse Eventsa			
LVEF		X	5.8.3.1
Hypertension	X	X	5.8.3.2
Prolonged QTc	X	X	5.8.3.3
Skin -Related Adverse Events (Except cuSCC)b or new primary melanomas			
Rash	X	X	5.8.4.1
Hand-Foot Skin Reaction	X	X	5.8.4.2
cuSCC	X	X	5.8.4.3
Other Adverse Events			
Pyrexia	X		5.8.5.1
Diarrhea	X	X	5.8.5.2
Renal Insufficiency	X	X	5.8.5.3
Visual Changes		X	5.8.5.4
Pneumonitis		X	5.8.5.5
Liver Chemistry Stopping Criteria	X	X	5.9.1

- a. For subjects enrolled in France please see [Appendix 9](#) and [Appendix 11](#) for additional dose modification guidelines
- b. Refer to Section [5.8.4.3](#) for management of cuSCC

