**When any of the liver chemistry stopping criteria 1 – 5 is met, do the following:**

- **Immediately discontinue subject from study treatment**
- Report the event to Novartis **within 24 hours** of learning its occurrence
- Complete the liver event CRF and SAE data collection tool if the event also meets the criteria for an SAE
  - All events of ALT  $\geq 3$ xULN and bilirubin  $\geq 2$ xULN (>35% direct bilirubin) (or ALT  $\geq 3$ xULN and INR >1.5, if INR measured; INR measurement is not required and the threshold value stated will not apply to subjects receiving anticoagulants), termed ‘Hy’s Law’, **must be reported as an SAE.**

- NOTE: if serum bilirubin fractionation is not immediately available, study treatment should be discontinued if ALT  $\geq$  3xULN and bilirubin  $\geq$  2xULN. Serum bilirubin fractionation should be performed if testing is available. If testing is unavailable, record presence of detectable urinary bilirubin on dipstick, indicating direct bilirubin elevations and suggesting liver injury.
- Complete the liver imaging and/or liver biopsy CRFs if these tests are performed.
- Perform liver event follow up assessments, and monitor the subject until liver chemistries resolve, stabilize, or return to baseline values as described below
- Follow up for overall survival is required following discontinuation from study treatment.
- Do not rechallenge with study treatment.

In addition, for subjects meeting liver stopping criterion 1:

- Make every reasonable attempt to have subjects return to clinic within 24 hours for repeat liver chemistries, liver event follow up assessments (refer to Section [5.9.1.1](#)), and close monitoring
- A specialist or hepatology consultation is recommended
- Monitor subjects twice weekly until liver chemistries (ALT, AST, alkaline phosphatase, bilirubin) resolve, stabilize or return to within baseline values.

For subjects meeting any of the liver stopping criteria 2 – 5:

- Make every reasonable attempt to have subjects return to clinic within 24-72 hrs for repeat liver chemistries and liver event follow up assessments (refer to Section [5.9.1.1](#))
- Monitor subjects weekly until liver chemistries (ALT, AST, alkaline phosphatase, bilirubin) resolve, stabilize or return to within baseline values;
- Subjects meeting criterion 5 should be monitored as frequently as possible.

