  - All events of possible drug-induced liver injury with hyperbilirubinae defined as ALT  $\geq$  3xULN and bilirubin  $\geq$  2xULN (>35% direct) (or ALT  $\geq$  3xULN and INR>1.5, if INR measured) termed ‘Hy’s Law’ events (INR measurement is not required and the threshold value stated will not apply to patients receiving anticoagulants).
  - **Note:** bilirubin fractionation is performed if testing is available. If testing is unavailable, record presence of detectable urinary bilirubin on dipstick indicating direct bilirubin elevations and suggesting liver injury. If testing is unavailable and a subject meets the criterion of total bilirubin  $\geq$  2xULN, then the event is still reported as an SAE. If INR is obtained, include values on the SAE form. INR elevations >1.5 suggest severe liver injury.
  - Any new primary cancers and treatment emergent malignancies (including squamous cell carcinoma and new primary melanoma) with the exception of basal cell carcinoma (BCC). BCC should be reported as an AE or SAE based on the discretion of the investigator.
  - Symptomatic LVEF decrease that meets stopping criteria or asymptomatic LVEF decrease that does not recover, as outlined as LVEF guidance (Section [5.8.3.1](#)).
  - Retinal pigment epithelial detachment (RPED) or retinal vein occlusion (RVO)

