**Table 23 Time Frames for Reporting SAEs and Other Events**

Type of Event	Initial Reports		Follow-up Information on a Previous Report	
	Time Frame	Documents	Time Frame	Documents
All SAEs	24 hours	SAE data collection tool	24 hours	Updated SAE data collection
Pregnancy	24 hours	Pregnancy notification	2 weeks	Pregnancy follow-up form
Cardiovascular or death event	Initial and follow up reports to be completed within one week of when the cardiovascular event or death is reported	"CV events" and/or "death" data collection tool(s) if applicable	Initial and follow up reports to be completed within one week of when the cardiovascular event or death is reported	Updated "CV events" and/or "death" data collection tool(s) if applicable
Liver Chemistry Abnormalities:				
ALT $\geq$ 3 x ULN PLUS total bilirubin $\geq$ 2 x ULN (> 35% direct) or ALT $\geq$ 3 x ULN and INR > 1.5, if INR measured	24 hours b	SAE data collection tool, liver event eCRF form, and liver imaging and/or biopsy	24 hours	Updated SAE data collection tool and updated liver event eCRF form c
ALT $\geq$ 8 x ULN; ALT $\geq$ 3 x ULN with hepatitis or rash or $\geq$ 3 x ULN but < 5 x ULN that persists $\geq$ 4 weeks	24 hours b	Liver event eCRF form c	24 hours	Updated liver event eCRF form c
ALT $\geq$ 5 x ULN PLUS total bilirubin < 2 x ULN	24 hours b	Liver event eCRF form does not need completing unless elevations persist for 2	24 hours	
ALT $\geq$ 5 x ULN PLUS total bilirubin < 2 x ULN that persists	24 hours b	Liver event eCRF form c	24 hours	Updated liver event eCRF form c
ALT $\geq$ 3 x ULN but < 5 x ULN PLUS total bilirubin < 2 x ULN	24 hours b	Liver event eCRF form does not need completing unless elevations persist for 4 weeks or subject cannot be		

Abbreviations: ALT = alanine transaminase; AST = aspartate aminotransferase; eCRF = electronic case report form; INR = international normalized ratio; SAE = serious adverse event; ULN = upper limit of normal.

- INR measurement is not required; if measured, the threshold value stated will not apply to subjects receiving anticoagulants.
- Novartis to be notified at onset of liver chemistry elevations to discuss subject safety.
- Liver Event Documents (i.e., "Liver Event CRF" and "Liver Imaging CRF" and/or "Liver Biopsy CRF", as applicable) should be completed as soon as possible.

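### Liver stopping criterion 1 in Section 5.9.1 omits the anticoagulant exception that the protocol attaches to the same ALT-plus-INR threshold in three other places

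*Protocol*

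**What the plan says.** Criterion 1 in Protocol Section 5.9.1 has two limbs. One is ALT ≥3xULN with raised, mainly direct bilirubin. The other is ALT ≥3 "xULN and INR >1.5, if INR measured". The note beneath it deals only with bilirubin fractionation. Meeting any of criteria 1 to 5 means immediate discontinuation. Table 3 marks its row "Liver Chemistry Stopping Criteria" for both dabrafenib and trametinib.

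The action list that follows in 5.9.1 repeats the threshold in a sub-bullet on SAE reporting and adds: "INR measurement is not required and the threshold value stated will not apply to subjects receiving anticoagulants". Section 7.4.2.2 defines the protocol-specific SAE with the same proviso: "INR measurement is not required and the threshold value stated will not apply to patients receiving anticoagulants". The Table 23 footnote reads: "INR measurement is not required; if measured, the threshold value stated will not apply to subjects receiving anticoagulants".

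Such subjects can be in the trial. Table 2, footnote a, states: "Subjects receiving anticoagulation treatment may be allowed to participate with INR established within the therapeutic range prior to enrollment". Section 6.1 permits anticoagulants such as warfarin. Section 6.3 allows therapeutic warfarin with sponsor approval and close PT/INR monitoring. It also reports that dabrafenib lowers warfarin exposure by 37%, and that exposure may rise when dabrafenib is reduced, interrupted or stopped.

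**The concern.** An INR above 1.5 serves in criterion 1 as a sign of liver impairment. In an anticoagulated subject it may reflect only the anticoagulant, and the three reporting statements recognise this. The stopping rule does not, so the same result is disregarded for SAE reporting through the INR limb and yet ends treatment.

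For a subject who meets no other criterion, the difference matters. Section 5.9.1.2 lets some subjects continue with weekly monitoring: those whose ALT has come down to 3 to <5xULN, with bilirubin below 2xULN and no hepatitis symptoms or rash. That section gives way to criteria 1 to 5, so criterion 1 overrides it. The subject stops, and the action list in 5.9.1 makes no rechallenge the default. Restart under 5.9.1.3 or 5.9.1.4 needs written sponsor approval, new consent and ethics approval where required. These are patients with melanoma brain metastases, for whom losing an active treatment without hepatic cause is a real cost.

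**Working it through.** **Text comparison.** The protocol states the ALT ≥3xULN plus INR >1.5 pair in four places.

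| Place | Function | Anticoagulant exception |
|---|---|---|
| 5.9.1, criterion 1 | stops treatment | no |
| 5.9.1, actions, SAE sub-bullet | SAE reporting | yes |
| 7.4.2.2 | SAE definition | yes |
| 7.4.2.6, Table 23 footnote | reporting time frames | yes |

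Does the exception in the 5.9.1 action list reach the stopping rule? That list orders discontinuation first. It then asks for the "SAE data collection tool if the event also meets the criteria for an SAE", which makes SAE status a separate test, and the exception sits under that test. On the literal text it therefore governs reporting only.

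**Will the INR condition be met?** Table 24 schedules INR at screening only, but Section 6.3 requires close PT/INR monitoring on therapeutic warfarin, so an on-study INR is likely to exist for those subjects. Table 2 limits PT/INR to ≤1.3xULN and then exempts anticoagulated subjects in therapeutic range. The exemption has a purpose only if their INR may exceed that limit. The dabrafenib–warfarin interaction can then move INR either way for reasons unrelated to the liver.

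**When does the INR limb alone decide?** Remove everything that the other criteria already stop:
- the bilirubin limb of criterion 1;
- ALT ≥8xULN (criterion 2);
- ALT 5 to <8xULN for two weeks or more (criterion 3);
- ALT ≥3xULN with hepatitis or hypersensitivity symptoms (criterion 4);
- ALT 5 to <8xULN that cannot be monitored weekly (criterion 5).

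What remains is a symptom-free subject without the bilirubin elevation, with ALT either 3 to <5xULN, or 5 to <8xULN for under two weeks with weekly monitoring possible.

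**How many subjects?** The plan gives no figure to reproduce and no rates for anticoagulation, INR or ALT. The following is illustrative.

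Inputs:
- planned subjects, N = 120 (Section 4.1.1);
- anticoagulated with INR >1.5: 2% to 10% (assumed);
- ALT ≥3xULN: 5% to 15% (assumed, independent of anticoagulation);
- treatment-related symptom rates at the 150/2 dose, n = 79 (Section 1.1.3.2): pyrexia 58%, skin toxicity including rash 42%, fatigue 38%, nausea 34%.

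Share with none of these four symptoms:
- independent: 0.42 × 0.58 × 0.62 × 0.66 = 0.0997
- full overlap: 1 − 0.58 = 0.42

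Expected cases = N × anticoagulated share × ALT share × symptom-free share:
- low: 120 × 0.02 × 0.05 × 0.0997 = 0.012
- high: 120 × 0.10 × 0.15 × 0.42 = 0.756
- without the symptom factor: 120 × 0.02 × 0.05 = 0.12 to 120 × 0.10 × 0.15 = 1.8

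For the 9 patients still on treatment according to the amendment rationale:
- with the symptom factor: 9 × 0.02 × 0.05 × 0.0997 = 0.0009 to 9 × 0.10 × 0.15 × 0.42 = 0.057
- without it: 9 × 0.02 × 0.05 = 0.009 to 9 × 0.10 × 0.15 = 0.135

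**Limits of these figures.** None of them subtracts the exclusions under criteria 2, 3 and 5 or the bilirubin limb, so on that account 0.756 and 1.8 are too high for the window described. The symptom factor errs the other way: its rates are cumulative, and symptoms need not coincide with the ALT rise. The 1.8 makes neither deduction and is a ceiling under the assumed rates.

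**The case against.** The strongest objection is that the absence cannot be fully established. Section 4.2.1 says that the liver stopping criteria are defined in Section 5.9.1 and Appendix 6, and 5.9.1.2 points to Appendix 6 for the stopping algorithm. That figure is not available here and may carry the exception. This stands as a limit: a reader might infer that the protocol nowhere exempts anticoagulated subjects from the stopping rule, and the documents as seen do not support that. It does not clear the text of 5.9.1, which would then disagree with its own appendix.

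Second, a site could infer the exception. It appears a few lines below criterion 1, in the action list for all five criteria, and is followed by a dosing instruction that begins "NOTE: if serum bilirubin fractionation is not immediately available, study treatment should be discontinued if ALT". Stopping and reporting text are therefore mixed there. This also stands, but a mandatory stopping rule should not depend on inference.

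Third, a stopping rule wider than the SAE definition may be deliberate caution. That is possible, but no rationale is given, and an INR that the protocol discounts as a reportable liver signal is weak grounds for stopping.

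Fourth, sponsor contact would catch the problem: therapeutic warfarin needs approval, Table 23 requires notification within 24 hours, and restart routes exist. This reduces the harm, but criterion 1 requires the stop at once.

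A reader might also infer a safety hazard or a threat to the trial's result. Neither follows. The rule errs towards stopping. The primary analysis in SAP Section 11.1 does not use INR or the liver stopping criteria, and the possible Hy's law definition in SAP Section 12.7.1 uses ALT, bilirubin and ALP without INR.

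**Conclusion.** The point holds as a minor inconsistency in the text of Section 5.9.1: one of four statements of the threshold lacks the exception, and it is the one that stops treatment. Whether the whole protocol lacks it depends on Appendix 6.

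The effect is confined to the management of anticoagulated subjects with ALT ≥3xULN who meet no other stopping criterion, probably one or two subjects at most. That size rests on assumed anticoagulation and ALT rates and on their independence; the conclusion about the wording does not.

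**What to change.** In criterion 1 of Section 5.9.1, directly after the words on INR being measured, insert the protocol's own clause: "INR measurement is not required and the threshold value stated will not apply to subjects receiving anticoagulants". Confirm that the Appendix 6 algorithm agrees, and that the INR item in Table 26, which is a factor to weigh before restart and not a bar to it, is read the same way. If the sponsor does want INR to stop anticoagulated subjects, one sentence in criterion 1 saying so would settle the matter instead.

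The cost is one clause and two checks, with no added procedures. The downside is that INR would no longer trigger a stop in anticoagulated subjects, leaving the bilirubin limb of criterion 1 and criteria 2 to 5 as their safeguards.

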**When any of the liver chemistry stopping criteria 1 – 5 is met, do the following:**

- **Immediately discontinue subject from study treatment**
- Report the event to Novartis **within 24 hours** of learning its occurrence
- Complete the liver event CRF and SAE data collection tool if the event also meets the criteria for an SAE
  - All events of ALT  $\geq 3$ xULN and bilirubin  $\geq 2$ xULN (>35% direct bilirubin) (or ALT  $\geq 3$ xULN and INR >1.5, if INR measured; INR measurement is not required and the threshold value stated will not apply to subjects receiving anticoagulants), termed ‘Hy’s Law’, **must be reported as an SAE.**

- NOTE: if serum bilirubin fractionation is not immediately available, study treatment should be discontinued if ALT  $\geq$  3xULN and bilirubin  $\geq$  2xULN. Serum bilirubin fractionation should be performed if testing is available. If testing is unavailable, record presence of detectable urinary bilirubin on dipstick, indicating direct bilirubin elevations and suggesting liver injury.
- Complete the liver imaging and/or liver biopsy CRFs if these tests are performed.
- Perform liver event follow up assessments, and monitor the subject until liver chemistries resolve, stabilize, or return to baseline values as described below
- Follow up for overall survival is required following discontinuation from study treatment.
- Do not rechallenge with study treatment.

In addition, for subjects meeting liver stopping criterion 1:

- Make every reasonable attempt to have subjects return to clinic within 24 hours for repeat liver chemistries, liver event follow up assessments (refer to Section [5.9.1.1](#)), and close monitoring
- A specialist or hepatology consultation is recommended
- Monitor subjects twice weekly until liver chemistries (ALT, AST, alkaline phosphatase, bilirubin) resolve, stabilize or return to within baseline values.

For subjects meeting any of the liver stopping criteria 2 – 5:

- Make every reasonable attempt to have subjects return to clinic within 24-72 hrs for repeat liver chemistries and liver event follow up assessments (refer to Section [5.9.1.1](#))
- Monitor subjects weekly until liver chemistries (ALT, AST, alkaline phosphatase, bilirubin) resolve, stabilize or return to within baseline values;
- Subjects meeting criterion 5 should be monitored as frequently as possible.

